The minimum sample size was determined using an priori power analysis. The analysis was based on existing research that reported small effect sizes in attitudinal change trials (Diane Morin et al., 2023; Varughese & Luty, 2010; Walker & Scior, 2013). The only trial on attitudinal change study in the context of Special Olympics was conducted by Diane Morin et al. (2023) with small Cohen's d effect sizes for the sensitivity or tenderness factor ($d = 0.32$) and interaction factor ($d = 0.25$). We anticipated a mean effect size of $d = 0.29$, calculated from these two factors, for our sample size calculation. We assumed a two-sided t -test, an alpha level of 0.05, and a statistical power of 80%. Using G*Power 3.1.9.7 (Faul et al., 2009), we calculated a total sample size of 296 participants. In addition, we assumed an average dropout rate of 48% after baseline measurement, given the literature on dropout rates for attitude change in Special Olympics settings of 34% (Sullivan & Masters Glidden, 2014) and of 63% in average online surveys for randomly selected samples (Wu et al. (2022)). The aim was therefore to achieve a total sample size of 700 participants.

Descriptive statistics are presented using mean and standard deviation (SD) for continuous variables (unless otherwise stated). We used t -tests, Mann-Whitney U tests, or Chi-square tests to compare differences between groups (e.g., intervention vs control), depending on the distribution of metric data and the level of measurement. Associations of missingness at follow-up with baseline characteristics were assessed using binary logistic regression models.

A general linear model was used for analyses. All models were derived from complete cases according to allocation. K. Scior (2011) published a study identifying age and education as significant predictors of attitudes toward people with intellectual disabilities. Additionally, prior contact through sports has been demonstrated to be associated with less negative behavioral and affective attitudes (Albaum et al., 2022). Consequently, all models were adjusted for age, education, participation in sports, physical activity with people with intellectual

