disabilities, and baseline outcomes. For sensitivity analysis, we further adjusted for gender, income, and work with people with intellectual disabilities. The literature for this three confounders is inconsistent (D. Morin, Rivard, et al., 2013; Scior, 2011; Slater et al., 2020). Furthermore, analysis were repeated after excluding outliers ($\pm 3SD$ away from the mean). The significance level was set at $p < 0.05$ (two-sided). The statistical analyses were performed using IBM SPSS Statistics (Version 30).

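### Every model uses complete cases despite an assumed 48% dropout, and no planned analysis would reveal dropout linked to the post-intervention score that differs between groups

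*Combined protocol and SAP*

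**What the plan says.** All of this is in the combined protocol and SAP, under Statistical analysis unless noted.

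- **Analysis set.** "All models were derived from complete cases according to allocation". No exception is made for the sensitivity models.
- **Expected loss.** "In addition, we assumed an average dropout rate of 48% after baseline measurement". The figure is taken from two literature rates: 34% in Special Olympics attitude research, and a rate "of 63% in average online surveys for randomly selected samples". "The aim was therefore to achieve a total sample size of 700 participants".
- **Missingness.** "Associations of missingness at follow-up with baseline characteristics were assessed using binary logistic regression models". The text gives this result no further use: no weighting, imputation, covariate selection or sensitivity analysis draws on it.
- **Main adjustment.** Age, education, sports or physical-activity contact with people with intellectual disabilities, and the baseline outcome.
- **Sensitivity analyses.** There are two. In one, "we further adjusted for gender, income, and work with people with intellectual disabilities". The other repeats the models without values more than 3 SD from the mean.
- **Outcome** (Primary outcomes). ATTID-SF factor means, with change assessed after the intervention and at 6 months. Higher scores are more negative attitudes.
- **Allocation** (Study design and participants). Towns were not randomised to the programme.

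**The concern.** The plan expects to lose about half its participants and analyses only those who remain. A baseline-adjusted complete-case contrast is sound if, given the model's covariates, staying in the study is unrelated to the outcome. That holds less readily at 6 months, because participants have by then given a post-intervention score. If that score relates to who answers the last survey, and does so differently in Host Towns and control towns, the 6-month contrast is biased.

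None of the described analyses would show this. The post score is not among the listed covariates, and the missingness regression looks only at baseline characteristics. Neither sensitivity analysis addresses missing follow-up. People who answered the post survey but not the last one drop out of the 6-month analysis, although they have supplied relevant data.

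A difference between groups is plausible. Only Host Towns had the June events, and their programme leaders and involved community members had workshops in August, before the November-December follow-up.

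**Working it through.** **Inputs from the documents:** dropout 34%, 63% and 48%; target 700; calculated total 296; d = 0.29; two-sided alpha 0.05; higher score is worse.

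**Assumed, not in the documents:** 1:1 groups; correlation 0.6 between baseline and each follow-up, and 0.7 between the post score and the 6-month score; 52% retention in each group; no true effect; the retention slopes below.

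**1. The plan's own figures.** (34 + 63)/2 = 48.5, given as 48%. Inflating the stated total gives 296/(1 - 0.48) = 569.2, so 570, not 700. A two-sided t-test on the stated inputs gives 376 in total, and 376/0.52 = 723.1, so 724. The figure 296 matches a one-sided test. That is a separate matter and does not affect this point.

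**2. Expected complete cases and two-sided power at d = 0.29.**

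| Dropout | Analysed | Power |
|---|---|---|
| 34% | 700 x 0.66 = 462 | 0.87 |
| 48% | 700 x 0.52 = 364 | 0.79 |
| 63% | 700 x 0.37 = 259 | 0.64 |

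**3. What the planned adjustment handles.** I take N = 700 and about 48% missing, with retention depending on the adjusted baseline score in one group only (log-odds 0.5 per SD). Over 3,000 simulated trials with no true effect, the mean bias is -0.002 SD and the rejection rate 5.2%. Dropout of this kind is dealt with.

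**4. Retention that depends on the post score.** The retention model is

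logit P(retained at 6 months) = c_g + b_g x post score (in SD),

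with c_g set to give 52% retention in each group g. Among those retained, the 6-month score is regressed on group and baseline. With 2 million simulated participants the simulation error is about 0.002 SD.

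| Slope, Host Towns | Slope, controls | Bias (SD) | Share of 0.29 |
|---|---|---|---|
| -0.3, -0.5 or -0.7 | the same | within 0.003 of zero | about 0 |
| -0.5 | -0.25 | -0.038 | 13% |
| -0.3 | 0 | -0.049 | 17% |
| -0.5 | 0 | -0.080 | 28% |
| -0.7 | 0 | -0.106 | 37% |

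The slopes are for retention. A negative slope means that people with worse attitudes are less likely to stay, so the Host Town completers look better than their group and negative bias favours the programme. Reversing the slopes, or placing them in the control group only, reverses the sign.

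**5. What using the post score recovers.** Imputing the 6-month score from baseline and post score within each group brings the bias in every row to within 0.003 SD of zero. This follows from the set-up: everyone has a post score, and retention depends on nothing else. Now suppose instead that 40% are lost at the post survey itself, in Host Towns depending on the score they would have given, with random loss afterwards down to 52%. For the three Host-Town-only slopes, the 6-month bias runs from about -0.04 to -0.09 SD with complete cases and from about -0.04 to -0.09 SD with imputation. There is no gain.

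**6. A simple scale for outcome-dependent loss.** With equal dropout in both groups, if the gap between dropouts and completers differs between groups by x SD, the full-sample contrast shifts by dropout x x. At 48%: 0.48 x 0.1 = 0.048 and 0.48 x 0.3 = 0.144 SD. The same gaps give 0.034 to 0.102 SD at 34% and 0.063 to 0.189 SD at 63%.

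**The case against.** The plan is not careless about dropout. It raised the recruitment target to allow for it, and power with 364 completers is still about 0.79. Losing half the sample is therefore planned for and is not in itself the defect. Adjustment for the baseline outcome, age, education and sports contact removes the bias that those variables would cause (step 3). These points stand.

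Four stronger readings are tempting and are not supported:

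- **That the 6-month effect is overstated.** The documents give neither dropout by group nor any relation between dropout and the post score. Such a relation is an assumption of the illustration. Equal slopes give no bias, and other patterns would work against the programme.
- **That a mixed model or imputation would remove the bias.** It would do so only for loss after the post survey that is explained by observed data. The 48% is not split by wave, so the number of people who could be recovered is unknown.
- **That the post-intervention contrast is helped in the same way.** No earlier post-intervention score exists to inform it.
- **That the extended model loses further people.** This depends on unanswered income, gender or work items, and no item non-response is reported. The text does not define complete cases as per wave or across waves, nor rule out a common set for both models.

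What the objection does not supply is any analysis that would test the complete-case result against informative dropout.

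**Conclusion.** The point holds as a gap in the analysis and should be addressed. It does not demonstrate bias. With about half the sample expected to be missing and groups that were not randomised, the plan relies on one missing-data assumption and never varies it.

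Under the assumed correlations and retention, the 6-month bias ranges from about zero to about -0.11 SD, depending entirely on how far the link between post score and retention differs between groups. The upper end is more than a third of the effect the trial was sized for. The range shows what is possible and is not an estimate for this trial. Confidence is high that the analysis is missing, and low on the size and direction of any bias.

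**What to change.** 1. For each ATTID-SF factor, fit a mixed model to all available waves (baseline, post, 6 months) with group-by-time terms and the baseline covariates. Alternatively, use multiple imputation carried out separately by group, including the post score, the extended-model covariates and the predictors found in the missingness regression. Because the groups are not randomised, entering baseline as a response makes the contrast a difference in change. Imputation followed by the planned model keeps the baseline-adjusted contrast.
2. Keep the complete-case model as a sensitivity analysis, and define whether complete means per wave or across waves.
3. Fit the main and extended covariate sets to the same participants or the same imputed data, so that a changed estimate reflects adjustment and not a changed sample.
4. State that the new analysis rests on MAR and that, for the 6-month contrast, it recovers outcome information only from people who answered the post survey and not the last one.
5. For outcome-dependent loss at the post survey, add a delta-shift sensitivity analysis in which the shift for non-responders differs by group. Step 6 gives a starting scale.
6. Report response counts by group and wave, so that readers can see how much step 1 can recover.

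The cost is modest analyst time and no new data. The drawback is a more complex model whose MAR assumption cannot be verified.

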Legacy of the Special Olympics World Games Berlin 2023

NCT Number: NCT05871450

03.07.2025

Study design and participants

This quasi-experimental trial was performed in urban and municipal areas throughout Germany. Adults of any gender, race/ethnicity were eligible for participation if they resided in one of the a priori selected communities, were at least 18 years of age and part of one of the three stakeholder groups. The recruitment period, including the baseline measurement, commenced on March 14th 2023 and concluded on June 8th, 2023. The intervention (Host Town Program) was conducted from June 12th to 15th, 2023. The post intervention measurement took place from June 26th to July 15th, 2023 and the 6-months follow up measurement from November 29th, 2023 to December 31st, 2023.

The intervention group comprised residents from Host Towns, while the control group consisted of residents from municipalities that had not applied to become Host Towns (prior to the initiation of the study, 216 municipalities were selected by Special Olympics to deliver the Host Town Program). Host Towns and Control towns were constituted through a random selection process, stratified by municipality size. Of note, random selection was only feasible within the group of the Control Towns, while allocation to the intervention was not at random (Host Towns were defined by Special Olympics; nonequivalent groups design). The selection of municipalities was conducted from a range of urban and rural communities, encompassing large cities, medium-sized towns, small towns, and rural communities, in accordance with the categorisation of city and community types as delineated by the Federal Institute for Research on Building, Urban Affairs and Spatial Development (Bundesinstitut für Bau-, Stadt- und Raumforschung., 2017).

Intervention

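### Neither the main nor the sensitivity model adjusts for stakeholder group or municipality size class, so an imbalance in either could bias this non-randomised comparison

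*Combined protocol and SAP*

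**What the plan says.** Under Study design and participants, the combined protocol and SAP sets two factors before the intervention starts:

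- **Municipality size.** "Host Towns and Control towns were constituted through a random selection process, stratified by municipality size". The municipalities came from four community types, "encompassing large cities, medium-sized towns, small towns, and rural communities". The next sentence limits this: random selection was possible only among Control Towns, because Special Olympics had defined the Host Towns.
- **Stakeholder group.** Eligible residents "were at least 18 years of age and part of one of the three stakeholder groups". The groups are not named, and no quota, matching or balancing by group is described.

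The same section states that "allocation to the intervention was not at random" and calls the design one of nonequivalent groups.

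Under Statistical analysis, a general linear model is fitted to complete cases: "Consequently, all models were adjusted for age, education, participation in sports, physical activity with people with intellectual" disabilities, with the baseline outcome completing the list. For sensitivity, "we further adjusted for gender, income, and work with people with intellectual disabilities". A further repeat drops outliers beyond 3 SD. No model contains municipality size or stakeholder group, and no analysis stratified by either is described.

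**The concern.** Random allocation would balance such factors on average. Here the described protection is the covariate list, and it leaves out the two characteristics that the study itself used to select towns and admit participants. The authors were willing to adjust widely: the sensitivity model includes three covariates for which they call the literature inconsistent. No reason is given for omitting the two design factors.

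If the arms differ in their mix of stakeholder groups or of city and rural residents, and these categories differ in later attitudes after allowing for baseline and the other covariates, part of that difference would be counted as an effect of the Host Town Program. The planned effect is small, so a modest bias could matter for both the estimate and the test.

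**Working it through.** **Step 1. Compare design and models.**

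| Factor | Role in the design | Main model | Sensitivity model |
|---|---|---|---|
| Municipality size (4 types) | Selection stratum for towns | Absent | Absent |
| Stakeholder group (3) | Eligibility condition | Absent | Absent |

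Both factors are fixed before the intervention, so neither is a mediator and adjusting for them is not over-adjustment.

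**Step 2. The plan's benchmark.** The planned effect is the mean of two published values: (0.32 + 0.25)/2 = 0.285, given as 0.29. It serves here only as a yardstick. The plan gives no figure for the mix of either factor by arm or for their relation to attitudes, so there is no plan figure for this bias to reproduce.

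**Step 3. Bias from an omitted two-level category.** Approximately,

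bias = (difference between arms in the category's share) × (outcome difference between categories, in SD, given the model's covariates).

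Both inputs are assumptions.

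| Imbalance | Conditional difference | Bias | Share of 0.29 | Two-sided type I error |
|---|---|---|---|---|
| 0.10 | 0.2 SD | 0.02 SD | 7% | 5.3% |
| 0.20 | 0.3 SD | 0.06 SD | 21% | 8.1% |
| 0.30 | 0.4 SD | 0.12 SD | 41% | about 18% |

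The last column uses a normal approximation with residual SD 1, independent observations and 148 per arm (the plan's 296, split equally by assumption). The shift is bias/√(2/148); for 0.06 this is 0.06/0.116 = 0.52, and the error is 1 − Φ(1.96 − 0.52) + Φ(−1.96 − 0.52) = 0.081.

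**Step 4. A milder set of assumptions.** Suppose the gap between categories is stable over time. Adjusting for a baseline score that correlates r with the outcome then leaves about gap × (1 − r). With raw gaps of 0.2 to 0.4 SD and r of 0.6 to 0.7 (all assumed):

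- Residual gap: 0.2 × 0.3 = 0.06 SD to 0.4 × 0.4 = 0.16 SD.
- Bias at 10 to 30 points of imbalance: 0.10 × 0.06 = 0.006 SD to 0.30 × 0.16 = 0.048 SD.
- Share of 0.29: 2% to 17%.

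Conversely, the conditional differences in Step 3 would need raw gaps of about 0.2/0.4 = 0.5 SD to 0.4/0.3 = 1.3 SD if they arose this way. The result depends on the inputs chosen.

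**Step 5. Cost of adjustment.** Size takes 4 − 1 = 3 parameters and stakeholder group 3 − 1 = 2, so 5 in all. With 296 participants and one parameter per existing term, residual degrees of freedom fall from 289 to 284, and the critical t stays at 1.968. That counts individuals. Size and arm are both constant within a town, so in an analysis at town level with T towns the degrees of freedom for the arm comparison would fall from T − 2 to T − 5. The number of sampled towns is not stated.

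**The case against.** The strongest reply is that municipality size was handled by design: the selection was "stratified by municipality size", presumably to make the arms comparable. This stands in part. Size may well be balanced between towns, and stakeholder group is the stronger half of the point. But the documents do not say that both arms drew the same proportions per stratum, and they restrict random selection to Control Towns. Balance between towns also does not carry over to responding residents, still less to complete cases after an assumed 48% dropout.

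Second, the baseline score, sports participation and work contact may act as proxies. They would reduce the bias, as Step 4 shows, but cannot be relied on to remove it. A baseline score does not deal with categories that change differently over time, and work contact enters only the sensitivity model.

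Third, the plan already has between-group comparisons and logistic models of missingness on baseline characteristics. These could describe an imbalance, but they do not name the two factors and do not adjust the effect.

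Fourth, the usual rule of including the strata comes from stratified randomisation, whereas these strata served to sample towns. That is fair. The argument here rests on confounding in a non-random comparison, not on that rule. Any gain in precision is unquantified and secondary.

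Fifth, adjustment is not free. The stakeholder groups are undefined and not stated to be mutually exclusive, the number of towns is unknown, and the text dated July 2025 is in the past tense with follow-up ending in December 2023, so a change now is probably post hoc. All of this stands and shapes the remedy.

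**Conclusion.** The omission is plain on the text: two factors fixed before the intervention are missing from every described model in a nonequivalent-groups comparison. The plan should deal with it, first for stakeholder group and then for size class.

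A reader might infer that the effect estimate is confounded. The documents do not show this. Confounding needs both an imbalance between arms and a relation to outcome beyond the existing covariates, and neither is reported. Nor is 7% to 41% of d = 0.29 an estimate of the bias. It follows wholly from assumed imbalances of 10 to 30 points and conditional differences of 0.2 to 0.4 SD, and milder assumptions give 2% to 17%. The supportable statement is that the bias cannot be estimated from the documents, could go either way, and on assumed values runs from negligible to a material fraction of the planned effect.

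**What to change.** - Add stakeholder group (three levels) and municipality size class (four levels) as fixed effects in the models for each of the five ATTID-SF factors at both post-intervention and 6-month follow-up.
- If the data have already been analysed, label this analysis post hoc and report it beside the specified model, so that readers can see whether the estimate moves.
- Tabulate both factors by arm at baseline and among complete cases at each time point. This would show directly whether an imbalance exists.
- Define the three stakeholder groups and say how a person who belongs to more than one is classified.

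The cost is about 5 degrees of freedom, the model reruns and one table. Both variables should already be held from selection and eligibility. The loss is negligible counted against individuals but larger for size class if few towns were sampled, so the number of towns per arm and size class should be reported too.
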